### 5.3.6 Other Considerations

#### 5.3.6.1 Safety

A subject who has an AE coded to the same preferred term more than once during the Extension Phase and the Core Study will be counted only once in the incidence calculations for that AE. Similarly, if a subject has more than one AE in a single system organ class (SOC), the incidence will be counted only once for that SOC. If a subject has the same AE more than once, the occurrence that is of greatest severity will be used in the calculation of the incidence of individual AE by severity. The AE considered most closely related to study treatment will be used in the calculation of incidence of individual AE by relationship.

If a subject has taken the same concomitant medication (as coded to preferred WHO-drug term) more than once, the subject will be counted only once in the tabulation.

#### 5.3.6.2 Efficacy

If no diary data is observed during a period, then the seizure frequency per 28 days for that period will be set to missing. Missing diary data should not be interpreted as equivalent to a non-missing record of zero.

## 5.4 Efficacy Analyses

Only “valid days” and “valid seizure counts” will be used in the calculations of seizure frequency per 28 days. A “valid day” is defined as the day where seizure counts information is present, that is, either a record with an answer of ‘No’ to the question ‘Did the subject experience any seizures?’ or a positive number of seizures for at least one of the seizure types collected. “Valid seizure counts” are the seizure counts that are read from the valid seizure days.

The baseline for a given seizure type (or total) is defined as seizure frequency per 28 days of the given type (or total) based on all valid seizure diary data dated before the first dose date

of perampanel. This means that the baseline will be based on all valid seizure diary data occurring during the Core Study Pretreatment Phase.

#### 5.4.1 Primary Efficacy Analyses

Not applicable.

#### 5.4.2 Secondary Efficacy Analyses

The percent change in seizure frequency per 28 days during the Core Study and Maintenance Period of the Extension Phase with respect to baseline assessment collected during the Pretreatment Phase of the Core Study will be summarized using descriptive statistics (n, mean, median, minimum, maximum and 95% confidence interval). The percent change in seizure frequency per 28 days are calculated for total seizure, POS total seizure and total complex partial seizure for POS cohort, for PGTC seizure, absence seizure, myoclonic seizure and total seizure for PGTC cohort and for Secondarily Generalized seizures for GTC cohort. Total Seizures is sum of all seizures, including POS, generalized and other seizures. Total POS Seizures is sum of all POS seizures, including simple partial seizures without motor signs, simple partial seizures with motor signs, complex partial seizures and complex partial seizures with secondary generalization. Secondarily Generalized seizures cohort is a subset of POS cohort.

The proportion of subjects who are seizure-free and the proportion of responders based on decrease from baseline (during the Pretreatment Phase) in 28-day seizure frequency of equal or greater than 25%, equal or greater than 50%, and equal or greater than 75% during Maintenance Period of the Extension Phase will be summarized using frequency count (number and percentage). If subjects complete the Extension Phase and have no seizure during the Maintenance Period, those will be treated as seizure-free.

The number of subjects with new seizure types compared to Baseline Period and Seizure history will be summarized.

The CGIC and CGIS will be summarized for each visit using frequency count (number and percentage).

For Japan submission, all of the analysis will be repeated for Japanese population.

#### 5.4.3 Other Efficacy Analyses

The score of EQ-5D-Y each items (Mobility, Looking after myself, Doing usual activities, Having pain or discomfort, Feeling worried, sad or unhappy) will be summarized for each visit using frequency count (number and percentage). The measurement and the change from baseline of EQ-5D-Y VAS at each visit will be summarized using descriptive statistics (n, mean, standard deviation, median, minimum and maximum).

## 5.5 Pharmacokinetic, Pharmacodynamic, Pharmacogenomic, and Other Biomarker Analyses

### 5.5.1 Pharmacokinetic Analyses

Not applicable.

### 5.5.2 Pharmacodynamic, Pharmacogenomic, and Other Biomarker Analyses

Not applicable.

## 5.6 Safety Analyses

All safety analyses will be performed on the Safety Analysis Set. Safety data will be summarized on an “as treated” basis using descriptive statistics (eg, n, mean, standard deviation, median, minimum, maximum for continuous variables; n [%] for categorical variables). Safety variables include TEAEs, clinical laboratory parameters, vital signs, 12-lead ECG results, C-SSRS, growth parameters, CBCL, LGPT, and EEG. Study Day 1 for all safety analyses will be defined as the date of the 1st dose of study drug.

### 5.6.1 Extent of Exposure

Exposure will be evaluated for the Safety Analysis Set.

Duration of Extension Phase exposure will be calculated as the number of week between the date the subject received the first dose of perampanel in the Extension Phase and the date the subject received the last dose of perampanel in the Extension Phase. Total perampanel exposure will be calculated as the number of week between the date the subject received the first dose of perampanel in Core Study and the date the subject received the last dose of study drug in the Extension Phase.

Modal dose, mean daily dose, maximum daily dose and last daily dose will be presented using summary statistics and frequency using categories of <4, 4, >4-<8, 8-<12, 12=<. Number and percent of subjects who down-titrated or discontinued study at maximum daily dose exposed will be summarized using frequency count (number and percentage).

### 5.6.2 Adverse Events

The AE verbatim descriptions (investigator terms from the CRF) will be classified into standardized medical terminology using the Medical Dictionary for Regulatory Activities (MedDRA). Adverse events will be coded to the MedDRA (version 18.1 or higher) lower level term (LLT) closest to the verbatim term. The linked MedDRA preferred term (PT) and primary system organ class (SOC) will also be captured in the database.

A TEAE is defined as an AE that:

- Emerges from the date of first dose of study drug in Core Study to 28 days after last end date of dose in prescribed dose entry in Extension Phase, having been absent at pretreatment (Baseline) in Core Study, or
- Reemerges during treatment, having been present at pretreatment (Baseline) in Core Study but stopped before treatment, or
- Worsens in severity during treatment relative to the pretreatment state in Core Study, when the AE is continuous.

Only those AEs that are treatment emergent will be included in summary tables. All AEs, treatment emergent or otherwise, will be presented in subject data listings.

TEAEs will be summarized using the safety analysis set. The incidence of TEAEs will be reported as the number (percentage) of subjects with TEAEs by SOC and PT. A subject will be counted only once within a SOC and PT, even if the subject experienced more than one TEAE within a specific SOC and PT. The number (percentage) of subjects with TEAEs will also be summarized by maximum severity (mild, moderate, or severe).

The number (percentage) of subjects with TEAEs will also be summarized by relationship to study drug (Yes [possibly related, probably related] and No [not related]).

AEs will be analyzed by the actual dose at AE onset.

The number (percentage) of subjects with treatment-related TEAEs will be summarized by SOC and PT. Treatment-related TEAEs include those events considered by the investigator to be related to study treatment.

The number (percentage) of subjects with TEAEs leading to death will be summarized by MedDRA SOC and PT. A subject data listing of all AEs leading to death will be provided.

The number (percentage) of subjects with treatment-emergent SAEs will be summarized by MedDRA SOC and PT. A subject data listing of all SAEs will be provided.

The number (percentage) of subjects with TEAEs leading to discontinuation from study drug will be summarized by MedDRA SOC and PT. A subject data listing of all AEs leading to discontinuation from study drug will be provided.

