than at weekly intervals, up to 8 mg/day for subjects not receiving concomitant EIAEDs or 12 mg/day for subjects receiving EIAEDs. With the exception of subjects enrolled in Japan, subjects receiving concomitant EIAEDs may undergo dose titration beyond 12 mg/day and up to 16 mg/day if they tolerate 12 mg/day and are deemed likely to benefit from a higher dose. Subjects enrolled in Japan who are receiving concomitant EIAEDs will undergo a Japan-specific dosing schedule (see below). The dose of perampanel during this dose titration will not exceed 12 mg/day. Subjects not receiving EIAEDs may receive dose higher than 8 mg/day and up to 12 mg/day if they tolerate 8 mg/day and are deemed likely to benefit from a higher dose. Subjects will be flexibly dosed on the basis of individual tolerability. The Titration Period is a duration of up to 11 weeks, during which multiple dose adjustments are allowed in order to identify each subject's optimum dose. Each study visit is based on the actual prior visit (eg, Visit 3 is completed 2 weeks \pm 3 days of Visit 2, Visit 4 is completed 3 weeks \pm 3 days of Visit 3, Visit 5 is completed 3 weeks \pm 3 days of Visit 4. (revised per Amendment 02) Subjects will remain on their optimum dose once it is achieved during the Titration Period. (revised per Amendment 01)

Dosing Schedule (Global) (revised per Amendment 01)

Week	Subjects on Concomitant EIAEDs (mg/day)	Subjects not on Concomitant EIAEDs (mg/day)
0	4	2
1	6	4
2	8	6
3	10	6
4	10	8
5	12	8
6	12	10
7	14	10
8	14	12
9	16	12
10	16	—

Dosing Schedule (Japan Only) (revised per Amendment 01)

Week	Subjects on Concomitant EIAEDs (mg/day)	Subjects not on Concomitant EIAEDs (mg/day)
0	2	2
1	4	4
2	6	6
3	6	6
4	8	8
5	8	8
6	10	10
7	10	10
8	12	12
9	12	12
10	—	—

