### 5.6.1 Extent of Exposure

The duration of treatment (Titration Period and Maintenance Period of the Core Study) will be calculated as the number of weeks between the date the subject receives their 1st treatment dose and the date the subject receives the last dose of treatment. These values will be used to summarize the extent of exposure to study medication.

Modal dose, mean daily dose, maximum daily dose and last daily dose will be presented using summary statistics and frequency using categories of  $< 4$ ,  $4$ ,  $>4-<8$ ,  $8-<12$ ,  $12=\leq$ . Number and percent of subjects who down-titrated or discontinued study at maximum daily dose exposed will be summarized using frequency count (number and percentage).

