### **AEs of special Interest**

A listing of subjects with AEs related to suicidality, identified by relevant Standardized MedDRA Query (SMQ) terms, will be provided. TEAEs of special interest listed below will be summarized by SOC and PT. SMQs will be used to identify relevant terms for the following TEAEs.

- TEAEs suggestive of abuse potential
- TEAEs related to alertness and cognition
- TEAEs related to psychosis / psychotic disorders
- TEAEs related to hostility/aggression

- TEAEs related to status epilepticus/convulsions
- TEAEs related to lab abnormalities
- Cardiac and ECG TEAEs
- TEAEs related to rash

TEAEs related to rash will be identified by medical review. Falls will be summarized for the Pretreatment Phase and Follow-up Period and will be summarized by actual dose of onset for the Titration and Maintenance Periods.

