### **AEs of special Interest**

A listing of subjects with AEs related to suicidality, identified by relevant Standardized MedDRA Query (SMQ) terms, will be provided. TEAEs of special interest listed below will be summarized by SOC and PT. SMQs will be used to identify relevant terms for the following TEAEs.

- TEAEs suggestive of abuse potential
- TEAEs related to alertness and cognition

- TEAEs related to hostility/aggression
- TEAEs related to psychosis/psychotic disorders
- TEAEs related to status epilepticus/convulsions
- TEAEs related to lab abnormalities
- Cardiac and ECG TEAEs
- TEAEs related to rash

TEAEs related to rash will be identified by medical review. Falls, regardless of causality, will be summarized for the treatment period (including Titration phase and Maintenance phase of the Core Study, as well as Maintenance through Follow-up Period of the Extension phase) by the actual dose at onset.

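### Falls and adverse events are to be summarised by dose at onset with no time at dose or children at risk planned, so those tables partly reflect how long children stay on each dose

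*SAP*

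**What the plan says.** There are two plans, one for the Core Study (Core SAP) and one for the Extension Phase (Extension SAP).

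- **All AEs.** Only the Extension SAP (5.6.2) has a general rule: "AEs will be analyzed by the actual dose at AE onset".
- **Falls.** In the Core SAP (5.6.2, AEs of special interest), falls "will be summarized by actual dose of onset for the Titration and Maintenance Periods"; Pretreatment and Follow-up falls are summarised apart from that. The Extension SAP takes falls from the Core Study onward, "as well as Maintenance through Follow-up Period of the Extension phase) by the actual dose at onset".
- **Metric.** Both SAPs (5.6.2): "The incidence of TEAEs will be reported as the number (percentage) of subjects with TEAEs by SOC and PT". Neither mentions a rate per unit of time.
- **Repeats.** Under Extension SAP 5.3.6.1, a subject with the same preferred term more than once over Core and Extension "will be counted only once in the incidence calculations for that AE". Rules follow for which occurrence sets severity and relationship, but none for which sets the dose.
- **Exposure.** In both SAPs (5.6.1), duration is one interval from first to last dose. For dose, "Modal dose, mean daily dose, maximum daily dose and last daily dose will be presented using summary statistics and frequency using categories"; the top category is 12 mg and over. Under the Protocol synopsis, children on enzyme-inducing drugs outside Japan "may undergo dose titration beyond 12 mg/day and up to 16 mg/day".

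Both SAPs (section 5) produce summaries by inducer status. Table shells and programming rules are in separate documents.

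**The concern.** In an upward-titration study the child-time at each dose is very unequal. Table 1 of the Protocol moves children up in steps of one or two weeks, and most of the remaining time is then spent at the dose where the child settles. After titration the dose can go down for intolerable events or up for expected benefit. A count or percentage of children with an event, sorted by dose at onset, therefore mixes hazard with time and with the number of children who reached that dose.

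Safety is the primary endpoint and there is no comparator arm, so dose patterns within the study are among the few internal clues to a dose-related harm. A table without time at dose can show a gradient that is not there, or hide one that is. Two smaller gaps add to this. A fall in the Extension Follow-up Period happens off drug, yet falls within a summary by dose at onset. A repeated event has no stated dose to be counted under.

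**Working it through.** The plan gives no figure to reproduce. The weeks at each dose come from Protocol Table 1. The hazards, dose mixes and down-titration below are assumptions for illustration. With weekly hazard h and w weeks at a dose, the share of children with at least one event at that dose is 1 − exp(−h·w), expected events per child are h·w, and the rate is events divided by child-weeks.

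**1. Weeks at each dose (Table 1)**
- No inducer, settling at 8 mg, 52 weeks: 1, 1, 2 and 48 weeks at 2, 4, 6 and 8 mg.
- Inducer, taken to 16 mg, 52 weeks: 1, 1, 1, 2, 2, 2 and 43 weeks at 4, 6, 8, 10, 12, 14 and 16 mg.
- No inducer, 23 weeks: 1, 1, 2, 19 if settling at 8 mg; 1, 1, 2, 2, 2, 15 if going to 12 mg.

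**2. False gradient: constant h = 0.005 per week, 52 weeks**
- No inducer: 4 mg, 1 − exp(−0.005 × 1) = 0.5%; 8 mg, 1 − exp(−0.005 × 48) = 21.3%. The 8 mg share of events is 48/52 = 92%.
- Inducer: 4 mg, 0.5%; 16 mg, 1 − exp(−0.005 × 43) = 19.3%.
- The rate is 0.50 per 100 child-weeks at every dose. The gradient is produced by time alone.

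**3. Real gradient: h = 0.01 below 12 mg and 0.03 at 12 mg, no inducer, 23 weeks, all treated children as denominator**

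Let p be the share going to 12 mg and q the share settling at 8 mg. Then
- 8 mg: q(1 − e^−0.19) + p(1 − e^−0.02) = 0.1730q + 0.0198p
- 12 mg: p(1 − e^−0.45) = 0.3624p

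| Dose mix | 8 mg | 12 mg |
|---|---|---|
| 70% at 8 mg, 30% at 12 mg | 12.7% | 10.9% |
| 10/40/50% at 4/8/12 mg | 7.9% | 18.1% |
| 10/30/60% at 4/8/12 mg | 6.4% | 21.7% |

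The last two mixes are the planning scenarios in Core SAP section 4, for Japan; Protocol Table 2 has the same steps as the non-inducer column of Table 1. With q = 1 − p the columns are equal at p = 0.1730 / (0.3624 + 0.1730 − 0.0198) = 0.336. The order reverses only when fewer than about 34% of children reach 12 mg.

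With children ever exposed at the dose as denominator, the 70/30 mix gives 12.7% against 36.2%, the right order.

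**4. Does a children-exposed denominator suffice?** Take h = 0.005 up to 8 mg, 0.010 at 10 mg and 0.020 at 12 mg. Every child spends 4 weeks at 12 mg and returns to 8 mg, giving 42 weeks in total at 8 mg over 52 weeks.
- 8 mg: 1 − exp(−0.21) = 18.9%, or 21.0 events per 100 children.
- 12 mg: 1 − exp(−0.08) = 7.7%, or 8.0 events per 100 children.
- Rates: 0.50 against 2.00 per 100 child-weeks.

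All children are exposed at both doses, so that denominator changes nothing, and a true fourfold rise appears reversed. The case drops straight from 12 to 8 mg for simplicity. One week at 10 mg on the way leaves 41 weeks at 8 mg and 1 − exp(−0.205) = 18.5%, so the conclusion is unchanged.

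**The case against.** A reader might infer that, as planned, a clear dose-hazard relation would come out flat or reversed. The documents do not support that. The sentence on AEs by dose at onset states no denominator, and the shells are elsewhere. The 23-week reversal needs both an all-subjects denominator and fewer than about 34% of children at 12 mg; under the Core SAP's own planning mixes the order is right. This stands as a limit on size. It does not remove the point, because step 4 shows that stating a children-exposed denominator is not enough without child-time.

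A reader might also infer that the AE tables pool 12 to 16 mg/day, or that use above 12 mg/day would be invisible. Neither follows. The bands are given only for exposure summaries, whose statistics include the maximum and are split by inducer status, so some use above 12 mg would show. What remains is that the frequency tables cannot say how many children received more than 12 mg/day.

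The plan also has another route to dose-response. Protocol 9.7.1.7.1 relates model-predicted average steady-state concentration to the most frequent AEs graphically, with modelling of any relation that emerges. That is a partial answer: it covers falls only if they are among the AEs chosen.

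On Follow-up falls, a note to Table 6 of the Extension SAP assigns AEs on or after discontinuation to the Follow-up period. It settles the period and not the dose, while the falls sentence still runs through Follow-up.

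**Conclusion.** The point holds in a limited form. The dose-at-onset tables (all AEs and falls in the Extension SAP, falls only in the Core SAP) have no planned time at dose and no planned count of children at risk, so they partly reflect time at dose. The size depends on assumption: 0.5% against 21.3% from a constant hazard of 0.5 per 100 child-weeks over 52 weeks, and reversal of a real rise under some dose mixes and dose histories. The weeks follow Table 1, except for the assumed return to 8 mg; no hazard comes from the documents.

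Overall TEAE incidence, which serves the primary endpoint, is not affected. This is an inexpensive descriptive improvement that complements the planned exposure-AE modelling.

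**What to change.** - **Dose-at-onset tables, both SAPs.** For each dose give children with an event, children ever exposed, child-weeks and events per 100 child-weeks, within the planned inducer-status split. State which dose takes a repeated event.
- **Exposure frequency tables (5.6.1, both SAPs).** Split the open top band into 12 mg/day and above 12 to 16 mg/day. State which dose categories the AE and falls tables use.
- **Extension SAP, falls.** Tabulate Follow-up falls separately as off drug, as the Core SAP does.

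The cost is programming. Modal dose, mean daily dose and dose at onset already require dated dose records, so no new data are needed. Cells above 12 mg/day will be small. The rates will still be affected by selection, because children who tolerate the drug move up and those who do not move down; a footnote should say they are descriptive and not estimates of a causal dose effect.

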### **AEs of special Interest**

A listing of subjects with AEs related to suicidality, identified by relevant Standardized MedDRA Query (SMQ) terms, will be provided. TEAEs of special interest listed below will be summarized by SOC and PT. SMQs will be used to identify relevant terms for the following TEAEs.

- TEAEs suggestive of abuse potential
- TEAEs related to alertness and cognition

- TEAEs related to hostility/aggression
- TEAEs related to psychosis/psychotic disorders
- TEAEs related to status epilepticus/convulsions
- TEAEs related to lab abnormalities
- Cardiac and ECG TEAEs
- TEAEs related to rash

TEAEs related to rash will be identified by medical review. Falls, regardless of causality, will be summarized for the treatment period (including Titration phase and Maintenance phase of the Core Study, as well as Maintenance through Follow-up Period of the Extension phase) by the actual dose at onset.

### 5.6.3 Laboratory Values

Laboratory results will be summarized using Système International (SI) units, as appropriate. For all quantitative parameters listed in [protocol Section 9.5.1.5.3 Safety Assessments \(Laboratory Measurements\)](#), the actual value and the change from baseline to each post baseline visit and to the end of treatment (defined as the last on-treatment value) will be summarized by visit using descriptive statistics. Qualitative parameters listed in [protocol Section 9.5.1.5.3 Safety Assessments \(Laboratory Measurements\)](#) will be summarized using frequencies (number and percentage of subjects), and changes from baseline to each post baseline visit and to end of treatment will be reported using shift tables. Percentages will be based on the number of subjects with both non-missing baseline and relevant post baseline results.

Laboratory test results will be assigned a low/normal/high (LNH) classification according to whether the value was below (L), within (N), or above (H) the laboratory parameter's reference range. For each laboratory parameter, shift from baseline (LNH) to each post baseline visit and at the end of treatment will be presented. Similar shift tables from baseline (LNH) to the highest/lowest post baseline value will also be presented.

The Sponsor's Grading for Laboratory Values ([Protocol Appendix 2](#)) presents the criteria that will be used to identify subjects with treatment-emergent markedly abnormal laboratory values (TEMAV). Except for phosphate, a TEMAV was defined as a postbaseline value with an increase from baseline to a grade of 2 or higher. For phosphate, a TEMAV was defined as a post baseline value with an increase from baseline to a grade of 3 or higher. The number and percentage of subjects with TEMAVs will be presented; each subject will be counted once in the laboratory parameter high and low categories, as applicable. Markedly abnormal laboratory values will be flagged in the subject data listings..

For ALT and AST analysis, the number of subjects with greater than 3 times, but less than 5 times the ULN and the number of subjects with greater than 5 times the ULN will be summarized. For bilirubin, a summary of the number of subjects with serum concentrations greater than 2 times the ULN will be created. These summaries will also be provided for the

maximum value in the treatment duration. In addition, the number of subjects who meet the criteria for Hy's Law will be summarized by visit and during the treatment duration. A subject will be determined to have met Hy's Law if AST or ALT is  $> 3x$  ULN, bilirubin  $> 2x$  ULN, and alkaline phosphatase  $< 2x$  ULN at a visit. The number of subjects who meet each of the criteria for Hy's Law during treatment (but not all necessarily at the same visit) will also be summarized.

